hsCRP	high-sensitivity C-reactive protein
IATA	International Air Transport Association
ICF	informed consent form
ICH	International Conference on Harmonisation
IFN	interferon
IL-6	interleukin-6
INR	international normalized ratio
IRB	institutional review board
LAB	LA Biomed/Harbor-UCLA
LDL	low-density lipoprotein cholesterol
LPC	Laboratory Processing Chart
Lp-PLA2	lipoprotein-associated phospholipase A2
NIH	National Institutes of Health
OHRP	Office for Human Research Protections
OI	opportunistic infection
PAT	peripheral arterial tonometry
PEG-IFN	pegylated interferon

RBV	ribavirin
RHI	reactive hyperemia index
RNA	ribonucleic acid
SAE	serious adverse event
sICAM-1	soluble ICAM-1
sP-selectin	soluble P-selectin
SVR	sustained virologic response
TC	total cholesterol
TG	triglycerides
WBC	white blood cell
UCLA-WW	UCLA-Westwood

SCHEMA

Clinical and Translational Science Institute Prospective Longitudinal Assessment of Coinfected Subjects with HIV/Hepatitis C for Endothelial Function Study (CTSI-PLACE Study)

DESIGN	Prospective, observational, longitudinal cohort of HIV/HCV coinfecting subjects matched to HIV monoinfected controls with primary cross-sectional analysis of baseline endothelial function and circulating cardiovascular biomarkers.
DURATION	Subjects will be on study for a minimum of 52 weeks. Those who initiate HCV treatment will be on study for at least 24 weeks after end of HCV treatment.
SAMPLE SIZE	A total of 120 subjects will be enrolled in the study (80 HIV/HCV coinfecting and 40 HIV monoinfected subjects).
POPULATION	Group A: 80 HIV/HCV coinfecting subjects Group B: 40 HIV monoinfected subjects All subjects ≥ 18 years of age without known CVD at baseline with CD4 cell count ≥ 200 cells/mm ³ and HIV-1 RNA < 50 copies/mL within 120 days of study entry and on stable antiretroviral therapy (ART) since the time of last CD4 and HIV-1 RNA measurement. Those with a HCV infection must have HCV RNA $\geq 10,000$ IU/mL. The two groups will be frequency matched based upon age, race, sex, diabetes, smoking status, hormonal therapy and statin use, and CD4 cell count at baseline.
PROCEDURES	Group A (HIV/HCV coinfecting) Baseline: All subjects will undergo baseline endothelial function testing and laboratory assays on study entry. Follow-up: Subjects who do not initiate HCV treatment will have follow-up endothelial function and laboratory testing at 1 year. Subjects who initiate HCV treatment will have follow-up endothelial function and laboratory testing at 4 weeks after completing HCV treatment. Group B (HIV monoinfected) Baseline: All subjects will undergo baseline endothelial function testing and laboratory assays on study entry. Follow-up: All subjects will have follow-up endothelial function and laboratory testing at 1 year.

¹ Group A, HIV/HCV coinfectd; Group B, HIV monoinfected

² Baseline assessments as described in section 6.1, including vital signs, medical history, medications, medical record abstraction, serum/plasma collection and processing for laboratories and storage, and PAT testing

³ HCV treatment may be initiated at any point following study entry

⁴ The chart abstraction visit will consist of data abstraction by study staff from the medical record for the preceding 6 months (from time of study entry).

⁵ Follow-up assessments as described in section 6.1. PAT and biomarker testing at 1 year for all subjects except those that initiate HCV treatment. For those that initiate HCV treatment, PAT and biomarker testing should occur at 4 weeks after end of HCV treatment. HCV-treated subjects should then continue to be followed until 24 weeks after end of HCV treatment and HCV viral load at 12 and 24 weeks after end of HCV treatment recorded (through medical record abstraction).

1.0 HYPOTHESIS AND STUDY OBJECTIVES

1.1 Hypotheses:

- 1.1.1 HCV is additive with HIV in promoting CVD risk through increased immune activation and inflammation.
- 1.1.2 Markers of endothelial function, inflammation, and thrombosis that are not produced by the liver will provide more accurate and novel biomarkers for assessment of CVD risk in HIV/HCV coinfecting persons.
- 1.1.3 Treatment of HCV in HIV/HCV coinfecting persons will improve endothelial function and reduce chronic immune activation and inflammation.

1.2 Primary Objectives

- 1.2.1 To establish a UCLA CTSI-wide cohort of demographically diverse HIV/HCV coinfecting and matched HIV mono-infected men and women with HIV suppressed on stable antiretroviral therapy (ART).
- 1.2.2. To determine the effect of HCV coinfection on endothelial function in the HIV-1-infected cohort at baseline.
- 1.2.3 To assess whether non-hepatic biomarkers of endothelial dysfunction, inflammation, and thrombosis (sICAM-1, sE-selectin, Lp-PLA2, IL-6, and D-dimer) are better correlates of endothelial function than traditional hepatic-derived biomarkers (hsCRP and lipids) in HIV/HCV coinfecting in cross-sectional assessment at baseline.

1.3 Secondary Objectives

- 1.3.1 To determine the effect of HCV coinfection on endothelial function in the HIV-1-infected cohort over one year of follow-up.
- 1.3.2 To assess whether non-hepatic biomarkers of endothelial dysfunction, inflammation, and thrombosis (sICAM-1, sE-selectin, Lp-PLA2, IL-6, and D-dimer) are better correlates of longitudinal endothelial function than traditional hepatic-derived biomarkers (hsCRP and lipids) in HIV/HCV coinfecting persons
- 1.3.3 To determine the effect of HCV coinfection on metabolic parameters (insulin resistance, cholesterol) in the HIV-1 infected cohort at baseline.
- 1.3.4 To determine the effect of HCV coinfection on metabolic parameters (insulin resistance, cholesterol) in the HIV-1 infected cohort over one year of follow-up.

1.4 Exploratory Objectives

- 1.4.1 To explore the effect of HCV viremia on endothelial function in HIV/HCV coinfecting persons.
- 1.4.2 To explore the effect of HCV viremia on circulating CVD biomarkers in HIV/HCV coinfecting persons.
- 1.4.3 To explore the effect of HCV viremia on metabolic parameters (insulin resistance, cholesterol) in HIV/HCV coinfecting persons.
- 1.4.4 To explore the effect of HCV coinfection on circulating plasma levels of endothelial, platelet, and T-cell microparticles in HIV-infected persons.

2.0 INTRODUCTION

2.1 Background

Hepatitis C virus (HCV) infection is a leading cause of morbidity and mortality among those with HIV-1. Non-liver related morbidity and mortality, including cardiovascular outcomes, are poorly characterized in HIV/HCV coinfection. All-cause mortality is increased in HIV patients with HCV coinfection, independent of HIV disease progression.¹ Not only liver-related, but non-liver related deaths may be reduced with HCV treatment.^{2,3} However, non-liver related outcomes in HIV/HCV coinfection remain poorly characterized. Large retrospective observational studies have suggested an increased risk of CVD events in HCV-infected individuals, both with and without HIV infection.⁴⁻⁶ The contribution of HCV to elevated CVD risk in HIV patients is unknown. Multiple potential mechanisms for increased CVD risk with HCV infection exist, including hepatic steatosis, insulin resistance, and diabetes mellitus.^{7,8} Chronic immune activation, implicated in HIV-associated accelerated atherosclerosis, is further increased with HCV coinfection.^{9,10}

Endothelial function, a predictor of CVD risk, has not been adequately characterized in HIV/HCV coinfection. Endothelial dysfunction mediates development and progression of atherosclerosis.¹¹ HIV-infected patients have impaired endothelial function compared to non-HIV-infected patients.¹² In a single small cross-sectional analysis by Masia et al, no difference was seen in endothelial function measured by brachial flow-mediated dilation (FMD) in HIV/HCV coinfecting versus HIV monoinfected persons, but interpretation of their findings is limited by confounding related to inconsistent HIV suppression, which has a clear impact on these measures.¹³ Peripheral arterial tonometry (PAT) is an established, non-invasive method for assessment of endothelial function that has been shown to both correlate with known CVD risk factors and predict CVD risk in multiple non-HIV infected populations.¹⁴⁻¹⁶ Its characteristics of reproducibility and reduced inter-operator variability in comparison to FMD make it an attractive tool for the assessment of CVD risk in HIV-infected persons.¹⁷

Routine CVD risk markers are altered with HCV infection and non-hepatically produced markers of endothelial dysfunction and inflammation may be better predictors of CVD risk in this patient population. Lipid and hsCRP levels are widely used for CVD risk

assessment.^{18,19} However, hsCRP and lipids are reduced in the setting of HCV-associated chronic liver disease,^{20,21} related to impaired hepatic function and an incompletely understood interaction between HCV and host lipid metabolism.²² Thus, routine markers may underestimate CVD risk in HCV coinfecting persons. Non-hepatic CVD biomarkers which may have improved predictive utility in HIV/HCV coinfection include: soluble ICAM-1 (sICAM-1), soluble E-selectin (sE-selectin), lipoprotein-associated phospholipase A2 (Lp-PLA2), D-dimer, and interleukin-6 (IL-6). In large prospective studies, levels of these biomarkers predicted future CVD events and were consistently associated with classical risk factors.²³⁻³⁴ Lp-PLA2 has never been described in HCV and minimal data exist for HIV-infected individuals.³⁵ A few studies have compared sICAM-1 and sE-selectin levels in HIV/HCV versus HIV- or HCV-monoinfected controls and found higher baseline levels with HIV/HCV coinfection,^{29,30,36} but none have appropriately controlled for key confounders such as HIV viremia or traditional CVD risk factors. One study attempted to correlate levels of vascular adhesion molecules with endothelial dysfunction by FMD, but interpretation of their findings is similarly limited by the heterogeneity of their cohort and significant confounding.¹³ Thus, the predictive utility of these markers remains unknown.

Microparticles (MPs) are a novel marker of endothelial dysfunction. MPs are cell membrane blebs produced by activated and injured cells that retain the cellular hallmarks of their parent cells.³⁷ While a stimulus such as infection or tissue injury is believed to trigger MP formation, MPs stimulate a “sterile,” self-propagating, inflammatory cascade. MPs are understudied in HIV infection, but T cell MP numbers correlate with severity of hepatic disease in HCV mono-infection,³⁸ and endothelial cell MP numbers correlate strongly with degree of endothelial dysfunction in the general population.^{39,40} Similar to peripheral blood mononuclear cells (PBMCs), MP phenotyping and quantification via flow cytometry allows for assessment of immune activation and cellular dysfunction, but MPs can be measured on frozen plasma and are not subject to the same viability concerns as PBMCs.

Successful HCV therapy may improve CVD outcomes. CVD risk factors such as hepatic steatosis and insulin resistance improve with HCV clearance.⁴¹⁻⁴⁴ A growing, though still small, body of literature describes reduction of levels of endothelial markers and inflammation in subjects who responded to HCV treatment as compared to those who did not.^{29,30,36} These studies did not include an accompanying, more direct surrogate vascular measure of CVD risk such as endothelial dysfunction by PAT or FMD. The clinical significance of the observed change in circulating biomarkers is unknown. Our study will be the first to address both gaps.

2.1 Rationale

In this era of aging coinfecting persons on effective ART, CVD and metabolic outcomes must be better characterized. There are no existing prospective, longitudinal cohorts designed to investigate endothelial function in this population. It is not widely recognized by clinicians that the hepatically-produced CVD risk markers used in routine clinical practice may be unreliable in coinfecting persons, and data characterizing non-hepatic markers in this population are lacking. Through a unique, multi-disciplinary collaboration between the four UCLA CTSI institutions, we will establish a HIV/HCV coinfecting cohort

diverse with respect to race/ethnicity, gender, socioeconomic class, and mode of HCV transmission, in a large catchment area, and for whom outcomes have not been described. The HIV/HCV cohort will be matched with HIV monoinfected controls, all with HIV suppression on stable ART, for cross-sectional and longitudinal evaluation of endothelial function, as well as improved characterization of both novel and traditional CVD risk biomarkers. We will conduct novel exploratory analysis of the effect of HCV treatment and virologic suppression on endothelial function. The project is intended to generate preliminary data for application for R01 or program project funding to continue the cohort and improve our understanding of CVD and metabolic outcomes with chronic HIV/HCV coinfection.

2.2 Study Population

There will be two study groups: Group A will be HIV/HCV coinfecting subjects and Group B will be HIV monoinfected subjects. All HCV coinfecting subjects will have evidence of ongoing HCV replication on study entry. The HIV/HCV group may include both HCV treatment-naïve subjects and treatment-experienced subjects who have failed prior HCV therapy, as ongoing HCV replication, irrespective of prior HCV treatment, is believed to be the primary driver of HCV-associated chronic inflammation and immune activation and end-organ disease. To control for the effect of HIV infection on the outcomes of interest, all subjects are to have undetectable HIV RNA (<50 copies/mL) and CD4 cell count ≥ 200 cells/mm³. All HCV genotypes are permitted in the study. Subjects who initiate HCV treatment following study entry are included to allow exploratory analysis of the potential benefit of HCV treatment and virologic clearance on CVD.

2.3 Selection of PAT as measure of endothelial function and correlate for CVD risk.

Endothelial dysfunction represents an early stage of coronary artery disease (CAD).⁴⁵ The presence of endothelial dysfunction in coronary or peripheral vessels constitutes an independent predictor of cardiovascular events.⁴⁶ Noninvasive measures of peripheral vascular endothelial function have been developed, but most are limited by operator dependency or complexity.⁴⁷⁻⁴⁹

PAT is a noninvasive technique to assess peripheral microvascular endothelial function by measuring changes in digital pulse volume during reactive hyperemia. PAT has favorable characteristics when compared to other noninvasive measures of peripheral vascular endothelial function with respect to reduced complexity, operator independence, and reproducibility.^{17,49}

Endothelial dysfunction is reversible and early detection of endothelial dysfunction may have therapeutic and prognostic implications. Multiple studies have demonstrated changes in endothelial function measured by PAT within 1 year or less, including with interventions.⁴⁹⁻⁵¹

3.0 STUDY DESIGN

This is a prospective, observational, longitudinal study of two groups, Group A, HIV/HCV coinfecting subjects and Group B, HIV monoinfected subjects. The HIV/HCV subjects

will be frequency-matched to the HIV monoinfected subjects by age (<40, 40-49, 50-54, and ≥55 years), race (white, black, other), sex at birth, diabetes (yes/no), smoking status (current or not), HMG Co-A reductase inhibitor (statin) and hormonal therapy use, and CD4 cell count (200-349 and ≥350 cells/mm³) at baseline. All subjects will be followed for a minimum of 1 year. A subset of the HIV/HCV coinfecting group are expected to initiate HCV treatment during this time and will be followed through up to 24 weeks following end of HCV treatment. All subjects will be included in baseline cross-sectional analysis of endothelial function, measured by peripheral arterial tonometry (PAT) and laboratory testing for circulating CVD biomarkers. All subjects will have follow-up PAT and laboratory testing and clinical follow-up. Those HIV/HCV coinfecting that do not begin HCV treatment and all HIV monoinfected will have follow-up PAT and laboratory testing at 1 year. Those HIV/HCV coinfecting who begin HCV treatment will have follow-up PAT and laboratory testing at 4 weeks after end of HCV treatment, but will be followed clinically for up to 24 weeks after end of treatment to capture complete HCV treatment response data.

4.0 SELECTION AND ENROLLMENT OF SUBJECTS

4.1 Inclusion Criteria

4.1.1 Men and women ≥ 18 years of age.

4.1.2 Hepatitis C status:

4.1.2.1 For HIV/HCV coinfecting participants:

4.1.2.1.1 Presence of chronic HCV infection, defined by presence of serum HCV RNA in a subject with HCV antibody for ≥ 180 days, or two documented HCV RNA positive results >180 days apart, or positive HCV RNA with biopsy demonstrating chronic hepatitis.

NOTE: Two separate antibody tests > 180 days apart are not required; only that the positive HCV antibody test should be ≥ 180 days ago, with current serum HCV viremia as outlined in section 4.1.2.1.2.

4.1.2.1.2 Serum or plasma HCV RNA level ≥ 10,000 IU/mL at any point prior to study entry and in the absence of intervening HCV treatment, by any laboratory that has a Clinical Laboratory Improvement Amendments (CLIA) certification or its equivalent.

NOTE: This must be a quantitative HCV RNA test, not a qualitative HCV RNA test.

4.1.2.2 For HIV monoinfected participants:

Absence of chronic HCV infection, defined as a negative HCV screening antibody (+/- undetectable HCV RNA) within 1 year prior to

study entry.

- 4.1.3 HIV infection, documented by any licensed rapid HIV test or HIV enzyme or chemiluminescence immunoassay (E/CIA) test kit at any time prior to study entry and confirmed by a licensed Western blot or a second antibody test by a method other than the initial rapid HIV and/or E/CIA, or by HIV-1 p24 antigen, or plasma HIV-1 RNA viral load.

WHO (World Health Organization) and CDC (Centers for Disease Control and Prevention) guidelines mandate that confirmation of the initial test result must use a test that is different from the one used for the initial assessment. A reactive initial rapid test should be confirmed by either another type of rapid assay or an E/CIA that is based on a different antigen preparation and/or different test principle (eg, indirect versus competitive), or a Western blot or a plasma HIV-1 RNA.

- 4.1.4 CD4+ T-cell count > 200 cells/mm³, and none less than 200 cells/mm³, during the 12 weeks prior to study entry, at any laboratory that has CLIA certification or its equivalent.
- 4.1.5 Plasma HIV-1 RNA < 50 copies/mL at screening, and none > 200 copies/mL, during the 12 weeks prior to study entry, at any laboratory that has CLIA certification or its equivalent.
- 4.1.6 On continuous and stable ART for at least 12 weeks with CD4+ T cell count and plasma HIV-1 RNA measurements as in 4.1.4 and 4.1.5. Changes in regimen prior to study entry are allowed as long as they were not for treatment failure, in which case subjects should be on the same ART regimen for at least 8 weeks prior to study entry with documented HIV RNA < 50 copies/mL on this regimen. Subjects should have no plans to change ART in the next 52 weeks.
- 4.1.7 Ability and willingness of subject to provide written informed consent.

4.2 Exclusion Criteria

- 4.2.1 Known cardiovascular disease, as defined by a self-reported history or medical record documentation of any of the following: myocardial infarction, angina pectoris, prior revascularization (coronary artery bypass graft, percutaneous coronary intervention), peripheral vascular disease, arrhythmias, congestive heart failure, congenital heart disease, cerebrovascular disease (stroke, transient ischemic attack).
- 4.2.2 Diabetes requiring insulin therapy or hemoglobin A1c $> 8\%$ within 6 months prior to study entry.

- 4.2.3 Inability to conform to the following drug interruptions for PAT testing, whether due to safety (determined by the investigator) or willingness: No caffeine for 24 hours prior; no nicotine for 4 hours prior; no recreational or prescription stimulant use for 24 hours prior; stopping of beta blockers, short-acting calcium channel blockers (CCBs), nitrates, angiotensin-converting enzyme inhibitors (ACE-Is), angiotensin-receptor blockers (ARBs), and renin-inhibitors for 24 hours prior; and stopping of long acting CCBs 48 hours prior to testing.
 - 4.2.4 Evidence of decompensated liver disease manifested by presence of or history of ascites, variceal bleeding, or hepatic encephalopathy.
 - 4.2.5 Other known causes of significant liver disease including chronic or acute hepatitis B, acute hepatitis A, hemochromatosis, or homozygote alpha-1 antitrypsin deficiency.
 - 4.2.6 Serious illness including acute liver-related disease and malignancy requiring systemic treatment or hospitalization within 12 weeks prior to study entry.
 - 4.2.7 Presence of active or acute AIDS-defining opportunistic infections (OIs) within 12 weeks prior to study entry, which may affect CVD biomarkers. A list of AIDS-defining opportunistic infections as defined by the CDC, can be found in Appendix B of the following document:
<http://www.cdc.gov/mmwr/preview/mmwrhtml/00018871.htm>
 - 4.2.8 History of major organ transplantation with an existing functional graft and on immunosuppressive therapy.
 - 4.2.9 History of known vascular disorder or autoimmune processes including Crohn's disease, ulcerative colitis, severe psoriasis, rheumatoid arthritis, and cryoglobulinemia that may affect vascular studies.
 - 4.2.10 Pregnancy.
 - 4.2.11 HCV treatment (any approved or investigational agents) within 24 weeks prior to study entry.
 - 4.2.12 Use of immune-based therapies or systemic corticosteroids which may affect vascular studies or inflammatory/endothelial biomarkers within 12 weeks prior to study entry.
- NOTE: Routine standard of care, including hepatitis A and/or B, human papilloma virus, influenza, pneumococcal, tetanus, and meningococcal vaccines are permitted if administered at least 14 days before biomarker blood collections and peripheral arterial tonometry examinations.**
- 4.2.13 Advanced renal insufficiency as defined by glomerular filtration rate (GFR) < 30 mL/min/1.73 m² or treatment by dialysis.

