5.0.3 Prohibited Medications

There are no prohibited medications specific to this study.

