6.3.6 Clinical Assessments

Vital Signs

Blood pressure and heart rate will be recorded at screening and entry.

Height

Height will be measured at entry.

Weight

Weight will be measured at entry and week 52 visit.

Waist Circumference

Waist circumference will be measured at entry and week 52/study discontinuation visit. Measure waist circumference at level of iliac crest in centimeters (cm).

Signs and Symptoms

At entry, all signs and symptoms that occurred within 42 days before entry must be recorded. At week 52/study discontinuation visit, all signs and symptoms that occurred within 42 days prior must be recorded.

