6.3.11 Stored Plasma and Serum for batched testing for biomarkers

Stored plasma and serum will be collected at the indicated visits (section 6.1) for centralized, batched testing at the UCLA Clinical and Translational Research Laboratory (CTRL) for the following biomarkers: hsCRP, fasting glucose, fasting insulin, fasting lipid panel, hsCRP, sICAM-1, sE-selectin, Lp-PLA2, IL-6, and D-dimer. Fasting glucose and fasting insulin will be performed for non-diabetic subjects only. Subjects must be fasting at least 8 hours (nothing by mouth except medications and water). If subjects indicate a non-fasting state, they should be asked to return in a fasting state within the required visit window (please refer to section 6.1 for more information regarding visit window). If that is not possible, a non-fasting specimen should be obtained the same day, and the non-fasting state should be recorded on the CRF. Stored plasma will be collected at the indicated visits (section 6.1) for centralized testing for endothelial, monocyte, and T-cell microparticles in the laboratory of [name] (UCLA Division of Infectious Diseases). Samples should be collected, processed, and stored on-site frozen at -70°C until shipped to UCLA-WW in accordance with the CTSI-PLACE Study Lab Processing Chart (LPC) (Appendix II). **Subjects should not have received vaccines within 14 days prior to plasma and serum collection.**

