prescribed or recreational stimulant use for 24 hours; vigorous exercise for 12 hours.
Subjects should not have received vaccines within 14 days prior to PAT testing.

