Correlation analysis (Pearson or Spearman) will be conducted to evaluate the association of each circulating biomarker as the predictor and RHI as a continuous outcome variable. Further correlation of biomarkers with each other and with RHI will be performed by use of correlation matrices. Multiple linear regression models will be used while controlling for confounders as in Aim 1 analysis, but with each biomarker as the primary independent variable to determine the contribution of each biomarker as a predictor of RHI. A final model will be constructed by including all significant biomarkers to predict RHI. The adjusted R-squared value will be used to indicate the predictive ability of the model. Similar analysis will be carried out in HIV-monoinfected subjects only to derive the RHI prediction model. The models for each cohort will be compared to each other for their predictive ability and differences in individual biomarker

significance in each cohort. This analysis will allow us to define whether non-hepatically-derived biomarkers have stronger correlation with RHI than hepatically-derived biomarkers.

9.4.3 Objective: To determine the effect of HCV co-infection and HCV virologic suppression post treatment on endothelial function and CVD biomarkers in the HIV-1-infected cohort over one year of follow-up.

Change in RHI and change in biomarkers from baseline to follow-up will be compared among 4 groups of subjects (HCV treatment responders and non-responders, untreated HIV/HCV subjects, and HIV controls). Boxplots will be used to visually display the difference among 4 groups. Pair-wise comparison will be carried out based on 2-sample t-test or Wilcoxon test. ANCOVA will be carried out to compare among 4 groups adjusting for baseline values and demographic characteristics and other baseline confounders. Adjusted comparison between any 2 groups will be estimated based on appropriate contrast. Correlation analysis will be carried out between change in biomarkers and change in RHI.

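### Exposures barred before entry because they may disturb the biomarkers or vascular tests are not guarded against when the same measurements are repeated at follow-up, and minor acute infection is guarded at neither visit

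*Combined protocol and SAP*

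**What the plan says.** Three exclusions in section 4.2 look back 12 weeks from study entry and no further:

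- 4.2.12: "Use of immune-based therapies or systemic corticosteroids which may affect vascular studies or inflammatory/endothelial biomarkers within 12 weeks prior to study entry". The reason given covers both the vascular tests and the biomarkers.
- 4.2.7: "Presence of active or acute AIDS-defining opportunistic infections (OIs) within 12 weeks prior to study entry, which may affect CVD biomarkers". The reason given covers the biomarkers.
- 4.2.6: "Serious illness including acute liver-related disease and malignancy requiring systemic treatment or hospitalization within 12 weeks prior to study entry". No measurement reason is given.

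PAT and the batched assays are repeated at week 52, or about 4 weeks after the end of HCV treatment (6.1). Several rules apply at each measurement: fasting for blood (6.3.11), and fasting plus abstention from caffeine, nicotine, vasoactive drugs, stimulants and hard exercise for PAT (6.3.13). Conception after entry leads to discontinuation (6.2.4). The only rule aimed at inflammation is the vaccine rule, stated for blood ("Subjects should not have received vaccines within 14 days prior to plasma and serum collection") and for PAT ("Subjects should not have received vaccines within 14 days prior to PAT testing").

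On drugs during the study, 5.0.3 says "There are no prohibited medications specific to this study". Some of the relevant facts are recorded. Section 6.3.6 says "At week 52/study discontinuation visit, all signs and symptoms that occurred within 42 days prior must be recorded" and uses the same look-back at entry. Section 6.3.7 records immune-based and anti-inflammatory therapy, and 6.3 records events meeting the serious-event definitions.

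In the analysis, 9.4.3 says "Change in RHI and change in biomarkers from baseline to follow-up will be compared among 4 groups of subjects". Its ANCOVA adjusts for baseline values, demographics and other baseline confounders. It also plans a correlation of biomarker change with RHI change, with no adjustment stated.

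**The concern.** The protocol's own reason for 4.2.7 and 4.2.12 is that these exposures can move what the study measures. That reason applies equally to the second measurement, but the protection stops at entry. Change is therefore taken from a screened baseline to a follow-up that is unscreened for the same exposures. The planned adjustment cannot repair this, because the exposures arise after baseline.

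There is also a smaller gap at both visits. A vaccine in the previous 14 days bars the measurement, while an ordinary acute infection in the same period does not, and no reason is given for the difference.

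At stake is precision: the spread of change in RHI and biomarkers (secondary endpoints) and, through minor infection alone, the baseline biomarker-RHI correlations of primary objective 1.2.3.

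**Working it through.** **Inputs from section 9.3.** Responders 27 against untreated 40, effect size 0.7, stated power 80%. Correlation 0.31 at n=80, stated power 80%. Two-sided alpha 0.05 (9.4.1).

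**Inputs assumed.** The documents give neither the share of subjects affected, f, nor the size of the shift, k, in SDs of the variable analysed. I use f = 5%, 10% and 20%, and k = 1 to 2.

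**Plan's figures reproduced.**

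- 27 against 40: noncentrality 0.7 × √(27×40/67) = 2.81. Power is 79.1% by noncentral t and 80.2% by the normal approximation.
- r = 0.31: Fisher z is 0.3205, times √77 gives 2.81. Power is 80.3%.

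Both agree with the stated 80%. Neither allows for exposures arising between visits.

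**Effect of contamination.** If a share f is shifted by k, with the same f in both groups, the variance is multiplied by V = 1 + f(1−f)k². The effect size, or the correlation when only the marker moves, is divided by √V. For f = 10% and k = 2: V = 1 + 0.09 × 4 = 1.36 and √V = 1.166. Then 0.7 becomes 0.60, and 0.31 becomes 0.27.

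| f | k | V | Power, 27 v 40 | r (true 0.31) | Power, n=80 |
|---|---|---|---|---|---|
| 5% | 1 | 1.048 | 77% | 0.30 | 78% |
| 5% | 2 | 1.190 | 72% | 0.28 | 73% |
| 10% | 1 | 1.090 | 76% | 0.30 | 77% |
| 10% | 1.5 | 1.203 | 71% | 0.28 | 72% |
| 10% | 2 | 1.360 | 66% | 0.27 | 67% |
| 20% | 1 | 1.160 | 73% | 0.29 | 74% |
| 20% | 2 | 1.640 | 58% | 0.24 | 58% |

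**Rescheduling against exclusion.** Dropping 10% of each group leaves about 24 and 36, with power 74%. Against 76%, 71% and 66% with the visits kept (k = 1, 1.5, 2), exclusion loses about 2 points, gains about 3, or gains about 8. Rescheduling loses no subjects and, where it succeeds, keeps the 79%.

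**Bias in a group contrast.** This is (f₁ − f₂) × k. It is zero if the rates are equal, 0.05 to 0.10 SD for 10% against 5%, and 0.15 to 0.30 SD for 20% against 5%. The documents give no rates by group.

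**Direction for objective 1.2.3.** I simulated 80 subjects in whom hsCRP and one non-hepatic marker correlate equally with RHI (0.31 in size, 0.3 with each other), with 5% to 15% infected and hsCRP shifted by 2 SD. Without contamination, hsCRP looks the weaker marker 50% of the time.

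- Infection moves hsCRP alone: about 58% to 67%.
- Infection also lowers RHI by 0.5 SD: about 36% to 44%.
- The other marker shifts by the same 2 SD and RHI does not move: 50%.

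**The case against.** The strongest reply is that the primary endpoint is baseline RHI, where the entry exclusions do apply. The longitudinal aims are secondary, in an observational study meant to supply preliminary data. The text contains no contradiction or wrong figure here, and the size of the problem rests wholly on assumed rates. At a 1 SD shift with 10% affected, the loss is 3 points of power, and excluding those visits would cost slightly more. All of this stands, and it limits the point to an inexpensive improvement.

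A reader might infer three stronger claims that the documents do not support:

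- *Inflammatory markers are pushed upward in every group, biasing the comparisons.* Corticosteroids and immune-based drugs need not raise these markers, and bias in a contrast needs unequal exposure rates, which are not given.
- *Objective 1.2.3 is tilted toward the hypothesis that non-hepatic markers do better.* IL-6 and D-dimer are on the non-hepatic side and may also respond to infection. The simulation goes either way, depending on what infection moves. Only minor infection reaches this baseline analysis.
- *Follow-up is protected against nothing but vaccines.* That is true of inflammatory exposures only; the fasting, abstention and pregnancy rules also apply.

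Another fair objection is that excluding follow-up visits by a post-baseline event can introduce selection. Acute liver-related disease, named in 4.2.6, may itself result from HCV. This is why exclusion belongs only in a secondary analysis.

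**Conclusion.** The point holds as one of avoidable noise. For 4.2.7 and 4.2.12 the protocol states a measurement reason and then does not apply it to the repeated measurement; 4.2.6 has the same time limit but no such reason. Minor acute infection is unguarded at both visits.

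With 10% of subjects affected and a shift of 1 to 2 SD, the loss is 3 to 13 points of power for 27 against 40 at 0.7 SD (79% to between 76% and 66%), and r = 0.31 falls to between 0.30 and 0.27. These sizes rest on an assumed rate and shift, on equal rates in the two groups and, for the correlation, on infection moving the marker but not RHI. No direction of bias is established. The primary comparison of baseline RHI is not touched by the follow-up gap.

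**What to change.** 1. Beside the vaccine rule in 6.3.11 and 6.3.13, state for entry and follow-up that blood and PAT are rescheduled within the existing visit window where possible if the subject reports recent acute infection, or recent systemic corticosteroid or immune-based therapy other than HCV treatment. The sponsor sets the look-back; the 14 days already used for vaccines is one example. Only the measurement moves, and no treatment is changed.
2. Ask about short courses at the visit, because the 7-day wording in 6.3.7 may be read to leave them out.
3. Where rescheduling is not possible, flag the visit. In 9.4.3, and in 9.4.2 for acute infection at baseline, report results with and without flagged visits. Keep the all-subjects analysis as the main one and name the other in advance as a secondary sensitivity analysis. Do not flag liver-related illness that may result from HCV.

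The cost is protocol and analysis-plan wording, one question at each measurement visit, a few rescheduled visits and one extra analysis. The downsides are slightly fewer subjects in the sensitivity set and possible selection, because the follow-up flag is post-baseline.
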